#### **4.4. End of Study Definition**

A participant is considered to have completed the study if he/she has completed all phases of the study, including the follow-up visit (Visit 11), approximately 28 to 35 days post last dose of double-blind investigator product (IP).

The end of the study is defined as the date of the follow-up last visit (Visit 11) of the last participant in the study.

### **5. STUDY POPULATION**

This study can fulfill its objectives only if appropriate participants are enrolled. The following eligibility criteria are designed to select participants for whom participation in the study is considered appropriate. All relevant medical and nonmedical conditions should be taken into consideration when deciding whether a particular participant is suitable for this protocol.

Prospective approval of protocol deviations to recruitment and enrollment criteria, also known as protocol waivers or exemptions, is not permitted.

#### **5.1. Inclusion Criteria**

##### **5.1.1. Inclusion Criteria for All Participants**

Participants are eligible to be included in the study only if all of the following criteria apply:

##### **Age and Sex:**

1. Male or female participants between the ages of 18 and 75 years, inclusive, at Visit 1 (screening).
  - Refer to [Appendix 4](#) for reproductive criteria for male ([Section 10.4.1](#)) and female ([Section 10.4.2](#)) participants.

##### **Type of Participant and Disease Characteristics:**

2. Participants who are willing and able to comply with all scheduled visits, treatment plan, laboratory tests, lifestyle considerations, and other study procedures, including the ability to perform self-monitoring blood glucose at a frequency deemed appropriate by the investigator.

### **Informed Consent:**

3. Capable of giving signed informed consent as described in [Appendix 1](#), which includes compliance with the requirements and restrictions listed in the informed consent document (ICD) and in this protocol.

#### **5.1.2. Additional Inclusion Criteria Only for Participants with T2DM**

1. Participants with T2DM who are treated with metformin. Metformin dose (at least 500 mg/day) must have been stable for at least 60 days prior to the screening visit (Visit 1).
2. HbA1c  $\geq 7.0\%$  and  $\leq 10.5\%$  at screening (Visit 1) as assessed by the study specific central laboratory. A single repeat is allowed, if deemed necessary.
3. Body mass index (BMI)  $\geq 27 \text{ kg/m}^2$ ; and a total body weight  $>50 \text{ kg}$  (110 lbs). Body weight must have been stable ( $<5\%$  change) for at least 90 days prior to screening (Visit 1) as per participant self-report.

#### **5.1.3. Additional Inclusion Criteria Only for Participants with Obesity without T2DM**

1. BMI  $\geq 30 \text{ kg/m}^2$ ; and a total body weight  $>50 \text{ kg}$  (110 lbs). Body weight must have been stable ( $<5\%$  change) for at least 90 days prior to screening (Visit 1) as per participant self-report.
2. HbA1c  $<6.5\%$  at screening (Visit 1) as assessed by the study specific central laboratory. A single repeat is allowed, if deemed necessary.
3. FPG  $<126 \text{ mg/dL}$  at screening (Visit 1) as assessed by the study specific central laboratory. A single repeat is allowed, if deemed necessary.

### **5.2. Exclusion Criteria**

#### **5.2.1. Exclusion Criteria for Only Participants with Obesity without T2DM**

1. Diagnosis of T2DM.

#### **5.2.2. Exclusion Criteria for All Participants**

Participants are excluded from the study if any of the following criteria apply:

#### **Medical Conditions:**

1. Other acute or chronic medical or psychiatric condition including recent (within the past year) or active suicidal ideation or behavior or laboratory abnormality that may increase the risk associated with study participation or IP administration or may interfere with the interpretation of study results and, in the judgment of the investigator, would make the participant inappropriate for entry into this study.

2. Any condition possibly affecting drug absorption (eg, prior bariatric surgery, gastrectomy, or any area of intestinal resection, active inflammatory bowel disease or pancreatic insufficiency).
3. Diagnosis of type 1 diabetes mellitus or secondary forms of diabetes.
4. History of myocardial infarction, unstable angina, arterial revascularization, stroke, New York Heart Association Functional Class II-IV heart failure, or transient ischemic attack within 6 months of screening (Visit 1).
5. Any malignancy not considered cured (except basal cell carcinoma and squamous cell carcinoma of the skin); a participant is considered cured if there has been no evidence of cancer recurrence in the previous 5 years.
6. Personal or family history of medullary thyroid carcinoma (MTC) or multiple endocrine neoplasia syndrome type 2 (MEN2), or participants with suspected MTC per the investigator's judgement.
7. Acute pancreatitis or history of chronic pancreatitis.
8. Symptomatic gallbladder disease.
9. Participants with a known medical history of active proliferative retinopathy and/or macular edema.
10. Participants with a known medical history of active liver disease (other than non-alcoholic hepatic steatosis), including chronic active hepatitis B or C, or primary biliary cirrhosis.
11. Participants with known history of human immunodeficiency virus (HIV).
12. History of major depressive disorder or history of other severe psychiatric disorders (eg, schizophrenia or bipolar disorder) within the last 2 years.
13. Any lifetime history of a suicide attempt.

**Prior/Concomitant Therapy:**

14. See [Appendix 8](#) for details regarding prohibited prior/concomitant medication.

**Prior/Concurrent Clinical Study Experience:**

15. Previous administration with an investigational drug within 30 days (or as determined by the local requirement) or 5 half-lives preceding the first dose of IP used in this study (whichever is longer).

16. Known prior participation in a trial involving PF-06882961 or known intolerance or hypersensitivity to a GLP-1R agonist.

**Diagnostic Assessments:**

17. A PHQ-9 score  $\geq 15$  obtained at V1, V2 or V3.

18. Response of “yes” to question 4 or 5, or on any behavioral question on the C-SSRS at V1, V2 or V3.

19. Screening (Visit 1) supine blood pressure (BP)  $\geq 160$  mm Hg (systolic) or  $\geq 100$  mmHg (diastolic), following at least 5 minutes of supine rest. BP should be measured in triplicate and the average of the 3 BP values should be used to determine the participant’s eligibility. **Note:** Participants with an arm circumference greater than the largest cuff size or those with a mid-arm circumference  $>52$  cm are not eligible.

20. Screening 12-lead ECG that demonstrates clinically relevant abnormalities that may affect participant safety or interpretation of study results (eg, baseline corrected QT interval [QTcF]  $>450$  msec, complete left bundle branch block [LBBB], signs of an acute or indeterminate-age myocardial infarction, ST-T interval changes suggestive of myocardial ischemia, second- or third-degree atrioventricular [AV] block, or serious bradyarrhythmias or tachyarrhythmias).

- If QTcF exceeds 450 msec, or QRS exceeds 120 msec, the ECG should be repeated 2 more times and the average of the 3 QTcF or QRS values should be used to determine the participant’s eligibility.

21. A positive urine drug test at screening.

- **Note:** Participants who have been prescribed opiates/opioids or benzodiazepine and report the use of these drugs to the investigator at screening (Visit 1) may be allowed to participate with notification to the sponsor.

22. Participants with ANY of the following abnormalities in clinical laboratory tests at Screening, as assessed by the study specific central laboratory and confirmed by a single repeat test, if deemed necessary:

- Aspartate aminotransferase (AST) or alanine aminotransferase (ALT) level  $\geq 2 \times$  upper limit of normal (ULN).
- Total bilirubin level  $\geq 1.5 \times$  ULN.
- Fasting C-peptide  $< 0.8$  ng/mL.
- TSH  $> 1.5 \times$  ULN.

- Serum calcitonin > ULN.
- Amylase or lipase > ULN.
- Fasting plasma glucose >270 mg/dL (15 mmol/L) at screening visit (Visit 1) or single-blind placebo run-in (Visit 2).
- Estimated glomerular filtration rate (eGFR) <60 mL/min/1.73m^2 as calculated by the Chronic Kidney Disease Epidemiology Collaboration (CKD-EPI) equation.

#### **Other Exclusions:**

23. Compliance of <89% (based on pill count) during the 2-week run in period, as assessed prior to randomization on Day 1 (Visit 3).
24. History of regular alcohol consumption exceeding 7 drinks/week for female participants or 14 drinks/week for male participants (1 drink = 5 ounces [150 mL] of wine or 12 ounces [360 mL] of beer or 1.5 ounces [45 mL] of hard liquor) within 6 months before screening (Visit 1).
25. Blood donation (excluding plasma donations) of approximately 1 pint (500 mL) or more within 60 days prior to dosing.
26. Unwilling or unable to comply with the criteria in the Lifestyle Considerations [Section 5.3](#) of the protocol.
27. Investigator site staff members directly involved in the conduct of the study and their family members, site staff members otherwise supervised by the investigator, or Pfizer employees, including their family members, directly involved in the conduct of the study.

### **5.3. Lifestyle Considerations**

#### **5.3.1. Dietary Restrictions**

1. Participants must abstain from all food and drink (except water) for at least 8 (preferably 10) hours prior to any body weight and blood sample collection(except post-dose PK samples).
2. IP must be administered BID with food, approximately 10 to 12 hours apart.
3. On scheduled morning visits to the site, from Visit 2 through Visit 9, participants should be instructed to arrive without having morning meal/breakfast, self-administration of IP, *and for participants with T2DM only*, morning dose of metformin for the given day. The above-mentioned medications will be administered with food at the site. Note: Participants may take their morning dose of

antihypertensive and/or lipid modifying medication per their usual routine, if applicable.

4. Participants will be counseled on appropriate dietary and lifestyle guidelines at Visit 2 and asked to maintain these guidelines throughout participation in the study.

- For participants with T2DM, counseling on dietary guidelines should be in accordance with local medical standards of care for patients with T2DM.
- For participants with obesity without T2DM, counseling on dietary guidelines should be in accordance with local medical standards of care for patients with obesity.
- **Note:** Participation in formal weight loss programs should be avoided during participation in this study.

### **5.3.2. Alcohol, Caffeine, and Tobacco**

- Intake of alcohol is permitted in moderation (refer to exclusion criterion [24](#) for acceptable amount of alcohol consumption).
- Caffeine containing products will be permitted during the study with the following restrictions: caffeine containing products may not be consumed within 1 hour prior to measuring vital signs and ECGs.
- Use of nicotine-containing products is permitted in this study with the following restrictions: nicotine-containing products may not be used within 1 hour prior to measuring vital signs and ECGs.

### **5.3.3. Physical Activity**

Participants will not be permitted to perform physically strenuous exercise (for example: heavy lifting, weight training, calisthenics and aerobics) within 48 hours prior to blood sample collections; walking at normal pace is permitted.

### **5.3.4. Contraception**

The investigator or his or her designee, in consultation with the participant, will confirm that the female participants have selected an appropriate method of contraception from the permitted list of contraception methods (see [Appendix 4 Section 10.4.4](#)) and will confirm that the participant has been instructed in its consistent and correct use. At time points indicated in the [SoA](#), the investigator or designee will inform the participant of the need to use highly effective contraception consistently and correctly and document the conversation and the participant's affirmation in the participant's chart (participants need to affirm their consistent and correct use of at least 1 of the selected methods of contraception). In addition, the investigator or designee will instruct the participant to call immediately if the selected

contraception method is discontinued or if pregnancy is known or suspected in the participant or partner.

#### **5.4. Screen Failures**

Screen failures are defined as participants who consent to participate in the clinical study but are not subsequently randomly assigned to IP at Visit 3. A minimal set of screen failure information is required to ensure transparent reporting of screen failure participants to meet the Consolidated Standards of Reporting Trials (CONSORT) publishing requirements and to respond to queries from regulatory authorities. Minimal information includes demography, screen failure details, eligibility criteria, and any SAE.

A participant who qualified for this study but did not enroll within the protocol prescribed screening period may be re-screened. All screening procedures must be repeated, and the participant assigned a new 8-digit study-specific subject identification (SSID) number.

Individuals who do not meet the criteria for participation in this study (screen failure) may not be rescreened.

### **6. STUDY INTERVENTION**

Study intervention is defined as any investigational intervention(s), marketed product(s), placebo, or medical device(s) intended to be administered to a study participant according to the study protocol.

For the purposes of this protocol, the term IP may be used synonymously with study intervention. For this study, the IP is PF-06882961 and matching placebo tablets; and will be administered orally, BID, with food.

Treatment phase IP will be packaged in blister cards containing blinded PF-06882961 or matching placebo for oral administration. Treatment assignment will be blinded, and blister cards will be labeled according to local regulatory requirements. For single-blind placebo run-in, tablets will be packaged in blinded-label blister cards according to local regulatory requirements.

Participants will continue taking their own metformin medication at the same total daily dose that was prescribed prior to study entry, except in circumstances where a dose change is deemed medically necessary.

## 6.1. Study Intervention(s) Administered

Intervention Name	PF-06882961	Placebo for PF-06882961
ARM Name	Active	Placebo
Type	Drug	Drug
Dose Formulation	Tablet	Tablet
Unit Dose Strength(s)	2.5 mg, 10 mg, 40 mg, and 100 mg	0 mg
Dosage Level(s)	Dose amount and frequency – refer to Figure 1	0 mg BID
Route of Administration	Oral	Oral
Investigational Medicinal Product (IMP) and Noninvestigational Medicinal Product (NIMP)	IMP	IMP
Sourcing	Provided centrally by the sponsor. Refer to the IP Manual.	Provided centrally by the sponsor. Refer to the IP Manual
Packaging and Labeling	Study intervention will be provided in blister packs. Each blister pack will be labeled as required per country requirement.  Blinded labels will be utilized for blister packs.	Study intervention will be provided in blister packs. Each blister pack will be labeled as required per country requirement.  Blinded labels will be utilized for blister packs.

### 6.1.1. Administration

All doses will be blinded and consist of 3 to 4 tablets administered BID via a blister pack.

Four (4) tablets BID will be administered during the 2-week single-blind placebo run-in and after randomization, during Weeks 1, 2 and 9 of dosing. Three (3) tablets will be administered BID during Weeks 3 to 8 and weeks 10 to 12 of dosing. Single-blinded blister cards will be used for the placebo run-in period. The dosing regimens after randomization will look the same across arms for each dosing window. Blister cards will look the same across all study arms and will contain the same number of tablets for the same time point in treatment.

After randomization during Weeks 1, 2 and 9 of dosing, participants will take 4 tablets of IP (PF-06882961 or matching placebo) in the morning with food and 4 tablets of IP in the evening with food, approximately 10 to 12 hours apart and at approximately the same time each day. Participants will take a total of 8 tablets of IP daily. The same dosing paradigm will be used during the single-blind placebo run-in period.

During Weeks 3 to 8 and Weeks 10 to 12 of dosing, participants will take 3 tablets of IP (in the morning with food and 3 tablets of IP with the evening with food approximately 10 to 12 hours apart and at approximately the same time each day. Participants will take a total of 6 tablets of IP (PF-06882961 or matching placebo) daily.

Participants will swallow the IP whole, and will not manipulate or chew the IP prior to swallowing. To maximize tolerability of PF-06882961 dose will be titrated over a period of 6 to 10 weeks.

The actual titration schemes for PF-06882961 to be used in this study are provided in Table 2 below. The regimen for Arm 5 (the placebo arm) will be placebo tablets administered BID with food in the morning and evening. Arms 1 to 7 are also depicted in [Figure 1](#).

**Table 2. Titration Schemes**

Week of Study	Arm 1	Arm 2	Arm 3	Arm 4	Arms 6 and 7
1	5 mg BID	10 mg BID	5 mg BID	10 mg BID	10 mg BID
2	10 mg BID	20 mg BID	5 mg BID	10 mg BID	20 mg BID
3	20 mg BID	40 mg BID	10 mg BID	20 mg BID	40 mg BID
4	40 mg BID	60 mg BID	10 mg BID	20 mg BID	60 mg BID
5	60 mg BID	80 mg BID	20 mg BID	40 mg BID	80 mg BID
6	80 mg BID	100 mg BID	20 mg BID	40 mg BID	100 mg BID
7	100 mg BID	120 mg BID	40 mg BID	60 mg BID	120 mg BID
8	120 mg BID	120 mg BID	40 mg BID	60 mg BID	140 mg BID
9	120 mg BID	120 mg BID	60 mg BID	80 mg BID	160 mg BID
10	120 mg BID	120 mg BID	60 mg BID	80 mg BID	180 mg BID
11	120 mg BID	120 mg BID	80 mg BID	80 mg BID	200 mg BID
12	120 mg BID	120 mg BID	80 mg BID	80 mg BID	200 mg BID

Morning dosing will occur with the food at the site at Visit 2 through Visit 9. Participants will be instructed to arrive at the site in the fasted state, bring their IP with them and to delay self-administration of IP and concomitant medications, if appropriate (as described in [Section 5.3.1](#)), on scheduled visit days until they arrive for their outpatient clinic visit.

Participants should be instructed that if they forget to take their morning dose at their usual time, they should take the missed dose as soon as possible (with food) on the day it was missed; however, there must be at least an 8-hour interval between the missed dose and the next dose. If a dose is missed and the interval to the next dose is less than 8 hours, the missed dose should not be administered.

Dosing and administration instructions along with the dosing diary, will be provided to participants to support at-home dosing of IP.

If participants schedule a visit prior to the protocol specified visit day they should be instructed by the investigator or site staff to continue dosing from the blister card they were dispensed previously.

## **6.2. Preparation/Handling/Storage/Accountability**

1. The investigator or designee must confirm appropriate temperature conditions have been maintained during transit for all study interventions received and any discrepancies are reported and resolved before use of the study intervention, as applicable for temperature-monitored shipments.
2. Only participants enrolled in the study may receive study intervention and only authorized site staff may supply or administer study intervention. All study interventions must be stored in a secure, environmentally controlled, and monitored (manual or automated recording) area in accordance with the labeled storage conditions with access limited to the investigator and authorized site staff. At a minimum, daily minimum and maximum temperatures for all site storage locations must be documented and available upon request. Data for nonworking days must indicate the minimum and maximum temperature since previously documented for all site storage locations upon return to business.
3. The investigator, institution, or the head of the medical institution (where applicable) is responsible for study intervention accountability, reconciliation, and record maintenance (ie, receipt, reconciliation, and final disposition records). All study interventions will be accounted for using an IP accountability form/record. All IP that is taken home by the participant, both used and unused, must be returned to the investigator by the participant.
4. Further guidance and information for the final disposition of unused study interventions are provided in the investigational product (IP) manual.
5. Any storage conditions stated in the SRSD will be superseded by the storage conditions stated on the product label.
6. Study interventions should be stored in their original containers and in accordance with the labels.
7. Site staff will instruct participants on the proper storage requirements for take-home study intervention.
8. Any excursions from the study intervention label storage conditions should be reported to Pfizer upon discovery along with any actions taken. The site should actively pursue options for returning the study intervention to the storage conditions described in the labeling, as soon as possible. Once an excursion is identified, the study intervention must be quarantined and not used until Pfizer provides permission to use the study intervention. It will not be considered a protocol deviation if Pfizer approves the use of the study intervention after the temperature excursion. Use of the

study intervention prior to Pfizer approval will be considered a protocol deviation. Specific details regarding the definition of an excursion and information the site should report for each excursion will be provided to the site in the investigational product (IP manual).

9. The sponsor or designee will provide guidance on the destruction of unused study intervention (eg, at the site). If destruction is authorized to take place at the investigator site, the investigator must ensure that the materials are destroyed in compliance with applicable environmental regulations, institutional policy, and any special instructions provided by Pfizer, and all destruction must be adequately documented.

Additional details about accountability, storage, destruction, and excursion reporting can be found in the IP manual.

### **6.2.1. Preparation and Dispensing**

The 2-week single-blind placebo run-in tablets will be dispensed at Visit 1 using an interactive response technology (IRT) drug management system. The same IRT drug management system will be used to dispense the IP from Visit 2 to Visit 8. A qualified staff member will dispense the IP via unique container numbers in the blister cards provided, in quantities appropriate for the study visit schedule. The participant should be instructed to maintain the product in the blister cards provided throughout the course of dosing and return the blister cards to the site at the next study visit.

## **6.3. Measures to Minimize Bias: Randomization and Blinding**

### **6.3.1. Allocation to Investigational Product**

Allocation of participants to treatment groups will proceed through the use of an IRT) system (interactive Web-based response [IWR]).

A randomization code using the method of random permuted blocks will be utilized to randomize eligible participants with T2DM treated with metformin in a 4:4:4:4:3 ratio (1 of 5 active dosing regimens of PF-06882961 or placebo) and non-diabetic participants with obesity in a 4:1 ratio (1 active dosing regimen of PF-06882961 or placebo) prior to the first dose of IP.

Participants will be stratified at randomization (Day 1) by population (T2DM vs. non-diabetic) and by biological sex (men vs. women).

The site personnel (study coordinator or specified designee) will be required to enter or select information including but not limited to the user's identification (ID) and password, the protocol number, and the participant number. The site personnel will then be provided with a treatment assignment, randomization number, and dispensable unit (DU) or container number when IP is being supplied via the IRT system. The IRT system will provide a confirmation report containing the participant number, randomization number, and DU or container number assigned. The confirmation report must be stored in the site's files.

IP will be dispensed at the study visits summarized in the [SoA](#).

Returned IP must not be re-dispensed to the participants.

The study-specific IRT reference manual and IP manual will provide the contact information and further details on the use of the IRT system.

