## 4. STUDY DESIGN

### 4.1. Overall Design

This Phase 2a, multicenter, randomized, double-blind, sponsor-open, placebo-controlled, parallel-group, study will assess tolerability, safety, and pharmacodynamics (PD) of BID administration of PF-06882961 in adult participants with T2DM who are treated with metformin. In addition, participants with obesity, without T2DM, will be enrolled to explore differences in tolerability, safety, pharmacokinetics and pharmacodynamics between participants with T2DM and participants without T2DM and to support clinical development in both T2DM and obesity.

[figure not shown]
For participants with T2DM, the metformin dose (at least 500 mg/day) must have been stable for at least 60 days prior to the screening visit (Visit 1) and should remain the same until the first follow-up visit (ie, Visit 10, Week 13-14), except in circumstances where a dose change is deemed medically necessary.

Following the screening period to confirm eligibility (up to 4 weeks), the study will consist of a 2-week single-blind placebo run-in period, prior to randomization on Day 1. Following randomization, participants with T2DM will be assigned to either the placebo arm or 1 of the 5 active treatment arms with PF-06882961. PF-06882961 doses will be titrated to a target dose of 80 mg BID in 2 arms, 120 mg BID in 2 arms, and 200 mg BID in 1 arm.

Following randomization, participants with obesity will be assigned to either the placebo arm or an active treatment arm with PF-06882961 with a target dose of 200 mg BID.

The treatment period will be 12 weeks, followed by an approximate 4-week follow-up. The total duration of participation in this study is approximately 18 weeks, not including the screening period. Dosing with PF-06882961 or placebo will occur BID with food in the morning and evening. Refer to Figure 1 for details of dose titration schemes per study arm, in which the doses depicted in Arms 1 to 7 are administered BID.

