**Figure 1. Dose Titration Schemes**

[figure not shown]
Assuming a 25% drop-out rate, approximately 140 participants will be randomly assigned to IP such that approximately 105 evaluable participants complete the study. Of these approximately 140 randomized participants, approximately 115 participants will have T2DM and approximately 25 will have obesity without T2DM. For participants with T2DM, approximately 20 participants will be allocated to each of the 5 active arms and approximately 15 participants to the placebo arm. For participants with obesity without T2DM, approximately 20 participants will be allocated to Arm 7 and approximately 5 participants to the placebo arm. To ensure balance between the groups, randomization will be stratified based on biological sex (men vs. women). There are no plans to replace withdrawn participants.

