## 9.2. Sample Size Determination

A sufficient number of participants will be screened to achieve approximately 140 participants randomly assigned to IP (approximately 120 participants in a PF-06882961 arm and approximately 20 evaluable participants in the placebo arm). For participants with T2DM, approximately 20 participants will be allocated to each of the 5 PF-06882961 arms and approximately 15 participants will be allocated to the placebo arm. For non-diabetic participants with obesity, approximately 20 participants will be allocated to a PF-06882961 arm (Arm 7) and approximately 5 participants to the placebo arm. Assuming a 25% drop-out rate for the entire study population, approximately 140 participants will be randomly assigned to IP such that approximately 105 evaluable participants complete the study.

Once approximately 140 participants have been randomized into the study, enrollment will be halted and any participants who have signed the ICD and initiated screening procedures at this stage may be permitted to continue the study process to completion/withdrawal.

The number of participants was selected empirically to provide a sufficient number of participants to assess and characterize the safety and tolerability of various titration schemes and target doses of PF-06882961 across the 2 populations.

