## 5.2. General Methods

The analyses related to the primary, secondary and exploratory endpoints will be based on the appropriate population for analysis (see Section 4).

Unless otherwise stated, all summaries and plots will be presented by treatment group. The following treatment group labels (or similar) will be used:

Arm	Strata	Treatment group label
5	T2DM	Placebo (T2DM)
5	Non-diabetic obesity	Placebo (non-diabetic obesity)
3	T2DM	PF-06882961 80 mg BID low, slow (T2DM)
4	T2DM	PF-06882961 80 mg BID high, slow (T2DM)
1	T2DM	PF-06882961 120 mg BID low, fast (T2DM)
2	T2DM	PF-06882961 120 mg BID high, fast (T2DM)
6	T2DM	PF-06882961 200mg BID (T2DM)
7	Non-diabetic obesity	PF-06882961 200mg BID (non-diabetic obesity)

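### The T2DM allocation ratio in Protocol 6.3.1 (4:4:4:4:3) has five terms for six randomised groups and cannot give the planned 5 × 20 + 15 = 115

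*Protocol*

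**What the plan says.** Protocol 6.3.1 describes a permuted-block code that will "randomize eligible participants with T2DM treated with metformin in a 4:4:4:4:3 ratio (1 of 5 active dosing regimens of PF-06882961 or placebo"). The same sentence randomises "non-diabetic participants with obesity in a 4:1 ratio (1 active dosing regimen of PF-06882961 or placebo"). Randomisation is stratified by population and by sex.

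The rest of the plan describes six T2DM groups:

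- Protocol 4.1 says that "participants with T2DM will be assigned to either the placebo arm or 1 of the 5 active treatment arms with PF-06882961".
- Protocol 4.1, in the text after Figure 1, gives the counts: "approximately 20 participants will be allocated to each of the 5 active arms and approximately 15 participants to the placebo arm". It gives the totals as "approximately 115 participants will have T2DM and approximately 25 will have obesity without T2DM". SAP 2.2 repeats both statements.
- Protocol 9.2 gives the same counts: "approximately 20 participants will be allocated to each of the 5 PF-06882961 arms and approximately 15 participants will be allocated to the placebo arm".
- The treatment-group table in SAP 5.2, read in full, labels six T2DM groups: placebo and Arms 1, 2, 3, 4 and 6. The Arm 6 label is "PF-06882961 200mg BID (T2DM"). Arm 7 and a second placebo group belong to the obesity population.

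Neither document gives a six-term ratio.

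**The concern.** The T2DM half of the sentence contradicts itself: its words describe six groups and its ratio describes five. The obesity half uses one term for each group (4:1 for one active regimen and placebo), so the T2DM ratio cannot be read as a shorthand that leaves a group out.

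The allocation ratio is a design figure, and 6.3.1 attaches it directly to the randomisation code. Per-arm counts appear elsewhere, but this is the only statement of the T2DM ratio. Anyone who specifies, verifies or reports the randomisation from this section has to decide which half of the sentence to follow. What is at stake is the step from this text to the randomisation list in the IRT system, which the documents do not show. The risk does not extend to power or precision, because Protocol 9.2 says the sample size was chosen empirically.

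**Working it through.** **Inputs**

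- T2DM ratio as printed: 4:4:4:4:3 (Protocol 6.3.1).
- T2DM groups: 5 active + 1 placebo = 6 (Protocol 4.1 and 6.3.1; SAP 5.2).
- Planned T2DM counts: 20 in each of 5 active arms and 15 on placebo (Protocol 4.1 and 9.2; SAP 2.2).
- Planned totals: 115 T2DM, 25 obesity, 140 in all; 25% drop-out; 105 completers (Protocol 4.1; SAP 2.2).
- Obesity ratio: 4:1 (Protocol 6.3.1).

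**Step 1. Reproduce the plan's totals from its per-arm counts.**

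- T2DM: 5 × 20 + 15 = 115.
- Obesity: 20 + 5 = 25, and 4:1 applied to 25 gives 25 × 4/5 = 20 and 25 × 1/5 = 5.
- All participants: 115 + 25 = 140. By treatment, 6 × 20 = 120 active and 15 + 5 = 20 placebo, again 140.
- Completers: 140 × 0.75 = 105.

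All of these agree with the documents. The only size-related figure left to test is the T2DM ratio.

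**Step 2. Apply the printed ratio.** The count for an arm is N × (its term) / (sum of terms). The sum is 4 + 4 + 4 + 4 + 3 = 19.

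- *Scaled to the planned arm sizes.* An active arm of 20 needs 20/4 = 5 participants per unit, and a placebo group of 15 needs 15/3 = 5. The total is 5 × 19 = 95, made up of 20, 20, 20, 20 and 15. The shortfall is 115 − 95 = 20.
- *Scaled to the planned total.* 115/19 = 6.05 per unit, which gives 115 × 4/19 = 24.2 in each of four arms and 115 × 3/19 = 18.2 on placebo. The sixth group receives nothing.
- *Read as the five active arms alone.* This gives 24.2 in four arms and 18.2 in the fifth, with no placebo group. The plan has five equal active arms and a placebo group.

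No reading of the five-term ratio gives five arms of 20 plus 15.

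**Step 3. Apply a six-term ratio.** For 4:4:4:4:4:3 the sum is 23, and 115/23 = 5 exactly. Active arms: 4 × 5 = 20, five times, so 100. Placebo: 3 × 5 = 15. Total: 115.

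**Step 4. Compare the two.**

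| | 4:4:4:4:3 | 4:4:4:4:4:3 | Plan |
|---|---|---|---|
| Groups | 5 | 6 | 6 |
| Sum of terms | 19 | 23 | – |
| T2DM total at 5 per unit | 95 | 115 | 115 |
| Placebo share | 3/19 = 15.8% | 3/23 = 13.0% | 15/115 = 13.0% |

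A block that holds the ratio exactly must be a multiple of the sum of terms: 19 under the printed ratio, 23 under the planned counts.

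**The case against.** The strongest reply is that this is an omitted 4 that any reader can restore. The sentence itself mentions five active regimens and placebo, the 20 and 15 counts appear three times across the two documents, and the SAP table lists all six groups. A five-term ratio cannot be assigned to six groups without someone asking which arm is missing. On this view the shortfall of 20 and the 15.8% placebo share would arise only if a whole active arm were dropped, which the rest of the plan rules out.

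Much of this stands. The intended ratio is recoverable, a literal use of the printed one is unlikely, and the percentages measure the discrepancy rather than predict an outcome. The documents show no misallocation. Nor do they say how the randomisation list was specified, so a direct path from this sentence to the list is not established. The arithmetic match to 20 and 15 also describes the ratio only: incomplete blocks within sex strata can shift the realised counts, and the plan says approximately throughout.

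Timing is a further limit. SAP version 2.0, dated 29 November 2021, cites blinded data reviews, so data were already being collected. The documents do not show whether randomisation was still open.

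None of this makes the printed ratio correct. Approximate counts can absorb a few participants, but not a missing arm.

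**Conclusion.** The point holds. The ratio in Protocol 6.3.1 lacks one term and contradicts its own sentence, Protocol 4.1 and 9.2, and SAP 2.2 and 5.2. It falls 20 T2DM participants short of 115, which is exactly one active arm. That the missing term is a 4 for the fifth active arm is an inference, but a firm one, because 4:4:4:4:4:3 is the ratio that reproduces the planned counts.

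The consequence is confined to the specification and reporting of the randomisation. Sample size, power, precision and the planned analyses are unaffected. It should be corrected, because a key design figure is wrong in the section that governs allocation and the remedy costs almost nothing.

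**What to change.** In Protocol 6.3.1, change the T2DM ratio to 4:4:4:4:4:3. Check that the IRT and randomisation-list specification has six T2DM groups in that ratio within each sex stratum. If the list has already been generated or used, check that list itself and record the result, so that the study report states the ratio actually applied.

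An optional wording change in Protocol 9.2: "approximately 20 evaluable participants in the placebo arm" appears in a sentence about randomised participants, and the figure is the randomised count (15 + 5 = 140 − 120). It could read as about 20 participants randomised to placebo, 15 with T2DM and 5 with obesity. It is not an error of number, since the protocol's evaluable set is everyone randomised who takes at least one dose.

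The cost is one ratio, optionally one phrase, and a check of the specification. It needs no extra participants and no change to any analysis.
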